11.3 Informed Consent

The informed consent/parental permission document must be approved by the SIRB and local HRPP prior to conducting any research activities. The informed consent/parental permission must be signed before any study procedures begin. ALL subjects participating must have a signed and dated consent form/parental permission form as part of the patient study file. An electronic or paper copy of the signed and dated consent form/parental permission form will be provided to the patient. At some institutions the form must also be signed and dated by the person obtaining the consent/parental permission.

Parental Permission

Subjects who are eligible for this study are under 18 years of age, and written permission from parents or legal guardians will be required for participation. After determining that a subject is eligible, the site investigator or designee will approach the parent or legal guardian to offer participation for their child in the study. The parent or legal guardian will be informed about the objectives of the study and the potential risks and benefits of participation. Subject will only be enrolled if their parent or guardian provides permission for their child to participate.

Protocol 1.00 ([name]) Page 31 of 44

Child Assent

Children who are capable of giving assent and who are alert and competent, will be asked, following an age-appropriate discussion of risks and benefits, to give assent to the study or further study procedures. Assent will be waived if the child is too young, has a severely reduced mental age, decreased level of consciousness, psychological problems, or other legitimate reasons as judged by

the Institutional Review Board.

Subject Consent

If a subject attains the age of 18 years during the study period, informed consent is required. Subjects who are capable of giving consent and who are alert and competent, will be asked, following an appropriate discussion of risks and benefits, to give consent to the study. For those with diminished mental capacity, a Legal Authorized Representative will be used.

11.4 Waivers Requested

Waiver of Authorization

A waiver of authorization is requested in order to be able to pre-screen/establish eligibility for subject prior to approaching, consenting, and enrolling a subject.

Waiver of Documentation of Informed Consent

The waiver is requested for subjects who reach the age of majority (18 years), after randomization.

11.5 Potential Risks

Loss of confidentiality of the subject is a potential risk of the study; however, safeguards are in place to protect against this.

11.6 Protections Against Potential Risks

To protect against a loss of confidentiality, the information gathered for this study will be coded with a special study number. A child's or parent's name and information that could identify them will be stored securely at the site where they were enrolled or in the study database.

11.7 Potential Benefits

There are no likely benefits anticipated from participation in this study; however, there is potential benefit to others because of the knowledge that may be gained from this research.

12 Data and Safety Monitoring Plan

12.1 Data Safety Monitoring Board (DSMB)

The study will have a Data Safety Monitoring Board (DSMB). The DSMB will have a charter, will approve the protocol prior to implementation, and will review interim analyses as applicable. The purpose of the DSMB is to advise the sponsors and Principal Investigator(s) regarding the continuing safety of study subjects and the continuing validity and scientific merit of the study. The DSMB is responsible for monitoring accrual of study subjects, adherence to the study protocol, assessments of data quality, performance of individual site, review of serious adverse events and other subject safety issues. There will be no formal stopping rules for efficacy or futility.

12.2 Safety Reporting

Hospital readmissions and medical errors are outcomes being collected for this study. These data constitute safety events and will provide an adequate method of assuring subject safety in the study. Safety events will be reported to the DSMB at regular meetings in a standard fashion and will be reviewed regularly at the DCC.

12.2.1 Definition of Medical Errors

Medical Errors Medical errors will be collected as described in the outcomes section above. Examples of medical errors captured within this outcome include parent-reported medication problems, miscommunications, diagnostic mistakes, delays in care, complications of care, and equipment problems. Medical errors will be categorized into levels of harm using the National Coordinating Council for Medication Error Reporting and Prevention Index for Categorizing Medication Errors Algorithm.⁷² This algorithm categorizes harms on a continuum from A–I, with the extremes being the absence of a true error (harm level A) and an error that resulted in patient death (harm level I). Harm levels F (initial or prolonged hospitalization required), G (life-sustaining intervention required but harm was not permanent), H (life-sustaining intervention required and harm was permanent), and I (death resulted) meet the definition of serious adverse events outlined below and will be reported as described below.

12.2.2 Definition of a Serious Adverse Event (SAE)

Serious Adverse Event (SAE): A serious adverse event (SAE) for this population is an error or event that:

- results in death; or
- is life-threatening (the patient was, in the view of the site investigator, in immediate danger of death from the event as it occurred); or
- prolongs an existing hospitalization; or
- results in persistent or significant disability or incapacity; or
- results in congenital anomaly/birth defect; or
- any other event that, based upon appropriate medical judgment, may jeopardize the subject's health and may require medical or surgical intervention to prevent one of the other outcomes listed in this definition.

Hospital readmission will already be captured as the primary outcome so these will not be reported as SAEs unless the PI determines this is necessary. SAEs will be captured between randomization and 14 days after hospital discharge.

12.2.3 Classification of an SAE (Relatedness, Severity, and Expectedness)

Relatedness: The suspected relationship between study interventions and any SAE will be determined by the site investigator using the criteria below. *Relatedness must be assessed by an investigator and may not be assessed by a research coordinator.*

Not Related: The event is clearly related to other factors, such as the subject's clinical state, therapeutic interventions, or concomitant drugs administered to the subject.

Possibly Related: The event follows compatible temporal sequence from the time of beginning the assigned study intervention, but could have been produced by other factors such as the subject's clinical state, therapeutic interventions, or concomitant drugs administered to the subject.

Probably Related: The event follows a reasonable temporal sequence from the time of beginning the assigned study intervention, and *cannot be reasonably explained* by other factors such as the subject's clinical state, therapeutic interventions, or concomitant drugs administered to the subject.

Severity: The severity, which is a measure of intensity, of clinical SAEs and laboratory abnormalities will be recorded by the site investigator and categorized. The following guidelines will be used to describe severity.

Mild: The event requires minimal or no treatment and does not interfere with the participant's daily activities.

Moderate: The event results in a low level of inconvenience or concern with the therapeutic measures. Moderate events may cause some interference with functioning.

Severe: The event interrupts a participant's usual daily activity and may require systemic drug therapy or other treatment. Severe events are usually potentially life-threatening or incapacitating. Of note, the term "severe" does not necessarily equate to "serious".

Expectedness of the Event: SAEs will be evaluated as to whether their occurrence was expected or unexpected. An SAE will be considered unexpected if the nature, severity, or frequency of the event is not consistent with the risk information described for the study intervention.

Expected: An event is considered expected if it is known to be associated with the underlying condition or is related to the study intervention and is mentioned in the protocol, informed consent, or other study documents. An event may be expected despite the study subject's clinical state immediately prior to the event. Any symptom related to the primary diagnosis for which the participant was initially hospitalized is expected. For example, symptoms that would be expected for all of the FAAN-C conditions are fevers, vomiting, and diarrhea. Expected symptoms for pneumonia are complaints like cough, shortness of breath, and trouble breathing. Expected symptoms for urinary tract infection are complaints like abdominal pain and dysuria. Expected symptoms for skin and soft tissue infections are complaints like pain, swelling, and redness at the site of infection. Expected symptoms for gastroenteritis are complaints like diarrhea.

Unexpected: An event is considered unexpected if there are no prior data linking this event with either the condition or intervention under study or an event that occurred unexpectedly in the course of treatment.

Treatment or Action Taken: For each SAE, the site investigator will record whether an intervention was required:

- Medical or surgical procedure
- Concomitant medication: started, changed, or discontinued
- Other, specify
- No action taken

Outcome of Event: Finally, the site investigator will record the clinical outcome of each SAE as follows:

- Death
- Recovered and the patient returned to baseline status
- Recovered with permanent sequelae
- Symptoms persist

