4.1 Selection of Outcomes

Selection of study outcomes was informed by the previously described focus groups involving parents of hospitalized children, hospitalists, and PCPs. Illustrative quotes that influenced selection of specific outcomes are presented in Table 4. Parents, PCPs, and hospitalists were clear that hospital readmission should be the primary outcome.

Page 14 of 44 Protocol 1.00 ([name])

Table 4: Selection of outcomes informed by focus groups

Participant	Representative participant responses to a question asking which outcomes would be important to study	Outcome added to FAAN-C
Parent	"The impact on parents, their time away from work"	Parent time
Parent	"We're all very invested in making sure things work out the best for our kids, often at the expense of our own health. Anxiety would be interesting to see because that plays into the situation and comes back to impact our kids as well."	Parent anxiety
Parent	"The one that really stands out to me is the number of times we have to go back to the hospital after being sent home."	Hospital readmission as the primary outcome
PCPs	"I feel like I develop my relationship with my patients and families through their well-child check-ups, not the sick or hospital follow-up appointments."	Well-child visits
PCPs	"I like to at least call my patients and parents after they are discharged from the hospital to maintain that relationship."	Telephone and electronic communications with medical providers
PCPs	"We worry that if kids don't follow-up, are they going to get so bad they need to be readmitted, so we hope that the follow-up prevents readmission."	Hospital readmission as the primary outcome
Hospitalist	"I think it helps to strengthen the relationship between the PCP and the family, so that they can see their PCP as not just the well doctor, but the well and sick doctor."	Usual place of medical care
Hospitalist	"I would look at health outcomes, readmission number one and emergency department utilization."	Hospital readmission as the primary outcome; total additional ambulatory visits

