4.5 Safety Outcomes

Safety outcomes are also listed in Table 5. Safety outcomes were selected with the goal of capturing adverse consequences (beyond hospital readmission, the primary outcome) that families might experience as a result of a recommendation for PRN follow-up, compared to a recommendation for automatic follow-up. A recommendation for PRN follow-up may result in those participants having to attend a greater number of other types of ambulatory visits (e.g., emergency department visits). The subset of non-primary care ambulatory visits will be measured because these visits have the potential to be more burdensome for participants (i.e., larger co-pays and urgent, less convenient visits), relative to a primary care visit. It is also possible that a recommendation for PRN follow-up could result in greater exposure to medical errors after hospital discharge (e.g., medication problems, complications of care), since another medical provider may not connect with the child and family shortly after hospital discharge. In addition to the primary outcome of all-cause hospital readmission, an additional safety outcome will be hospital readmissions related to the index infection. All safety outcomes are measured by parent report, from the time of hospital discharge

until the specified time after discharge.

Table 5: Secondary, exploratory, and safety outcomes

Outcome	Definition	Expected outcomes type for analysis ^a
	Secondary outcomes	
Medical interventions	Proportion of participants who receive either a laboratory test, imaging test ^b , or a new medication within 14 days of hospital discharge	Binary
Child health-related quality of life	Mean health-related quality of life score 7 days after hospital discharge, measured by the Impact on Activities and Routines instrument	Normal
	Exploratory outcomes	
Cost burden	Mean total costs to parents (missed income and expenses) related to the participant's illness within 14 days of hospital discharge, measured by the cost burden survey in Chang et al ⁴⁹	Binomial- Gamma hurdle
Child time	Mean number of hours of school or daycare missed by the participant within 14 days of hospital discharge as a result of their medical needs	Over-dispersed Binomial
Parent time	Mean number of hours spent away from responsibilities (work or non-work related) by parents within 14 days of hospital discharge as a result of their child's medical needs	Normal or Gamma

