12.2.6 Monitoring Serious Adverse Events

A qualified physician will be designated to fulfill the function of the medical monitor for this study. Site investigators and/or research coordinators will report serious adverse events to the Data Coordinating Center within 24 hours of becoming aware of the event. A detailed completed report will be required to be sent to the Data Coordinating Center within 3 working days of the event, and the medical monitor will assess all serious adverse events reported from site investigators.

For each of these serious adverse events, the site investigator will provide sufficient medical history and clinical details for a safety assessment to be made with regard to continuation of the trial. The medical monitor will sign off on each SAE report after review. All SAE reports will be retained at the Data Coordinating Center, and all SAE reports will be available for review by DSMB members and PCORI staff. The SAE reporting process may be incorporated into the Electronic Data Capture System in use for the study.

In the unlikely event that the medical monitor believes an unexpected and study-related SAE warrants emergent cessation of enrollment in the trial, the DSMB chairperson will be immediately consulted. If the DSMB chairperson concurs with the judgment of the medical monitor, or if the DSMB chairperson cannot be reached expeditiously, the Data Coordinating Center will notify the study investigator ([name]) and all site investigators to cease enrollment in the trial.

In accordance with local IRB requirements, the site investigator may be required to report such events to the IRB in addition to notifying the Data Coordinating Center.

After notification of the PCORI Program Official or Project Officer, and the DSMB chairperson, of *serious, unexpected, and study-related* adverse events or unanticipated problems (UP), decisions will be made whether to continue the study without change, and whether to convene the entire DSMB for an emergent meeting. If a decision is made to suspend enrollment in the trial, this will be reported to the study investigator ([name]) and all clinical investigators, who will be instructed to report this to their local IRB.

The DSMB will review medical errors and serious adverse events during scheduled DSMB meetings. The Data Coordinating Center will prepare a Summary Report of medical errors and serious adverse events.

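### The relatedness classes in Section 12.2.3 set the child's clinical state against the intervention, so an SAE that is progression of the index infection can be graded Not Related

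*Protocol*

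**What the plan says.** Relatedness of each SAE to the study intervention "will be determined by the site investigator using the criteria below" (Section 12.2.3). There are three classes:

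- **Not Related:** "The event is clearly related to other factors, such as the subject's clinical state", with treatments and other medication given as further examples.
- **Possibly Related:** the timing is compatible with the start of the assigned intervention, "but could have been produced by other factors such as the subject's clinical state" or by the other factors on the same list.
- **Probably Related:** the timing is reasonable and that same list of factors cannot reasonably account for the event.

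Section 12.2.4 has every SAE after randomization graded this way, and counts worsening of a condition already present as a new SAE if it meets the definition.

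The grade feeds two escalation routes. An unanticipated problem (Section 12.2.5) must be unexpected and at least possibly related. Section 12.2.6 sets the condition for halting enrollment: "In the unlikely event that the medical monitor believes an unexpected and study-related SAE warrants emergent cessation of enrollment in the trial". It uses a similar condition for notifying the funder and the DSMB chairperson, which leads to the decision whether to convene the full board.

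Elsewhere the protocol describes how PRN follow-up might do harm. In Table 4 (Section 4.1) a primary care provider asks, of children who are not followed up, "are they going to get so bad they need to be readmitted". Section 4.5 foresees more medical errors "since another medical provider may not connect with the child and family shortly after hospital discharge".

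**The concern.** The three classes suit an agent that produces events directly. For such an agent, the patient's underlying illness is a competing explanation, and the more clearly it explains the event, the less the agent is implicated.

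That logic does not carry over to a recommendation about a visit. If PRN follow-up harms a child, the likely course is that the infection worsens and is recognized or treated later than it would have been. The infection is then the route by which the harm arrives. A scale that counts it as an alternative cause pushes the events of most interest towards Not Related.

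At stake is whether an individual serious event reaches the pathways in Sections 12.2.5 and 12.2.6, all of which require some degree of relatedness.

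**Working it through.** No arithmetic applies: the protocol states no figure on this point and none is needed. The check applies the three classes to one case and then traces where the grade is used.

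**Step 1. One case against the three classes.** Suppose a child in the PRN arm has no visit, the index infection progresses several days after discharge, and the child dies or is in immediate danger of death. The infection clearly explains the event.

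| Class | Test | Result |
|---|---|---|
| Not Related | Clearly related to clinical state | Met |
| Possibly Related | Compatible timing; clinical state could have produced it | Met |
| Probably Related | Clinical state cannot reasonably explain it | Not met |

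Two classes apply at once, and the strongest is closed. Not Related and Possibly Related name the same other factors, so the only thing separating them is how sure the investigator is that the infection was responsible.

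**Step 2. Does the scale separate avertable events from the rest?** Take two such children, one whose course a visit would have changed and one whose course it would not. Timing and clinical state are the same, so the available grades are the same. No class asks whether a visit, or its absence, made a difference.

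**Step 3. The automatic arm.** Section 2.2 gives overtreatment as the possible harm of automatic follow-up. The list of other factors also contains therapeutic interventions and concomitant drugs. Harm from a treatment started at a follow-up visit can therefore be graded Not Related on the same reading. The problem is not confined to one arm.

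**Step 4. Who grades.** The site investigator does. Section 7.2 says medical providers cannot be blinded, and Section 8.4 has the inpatient team told the assignment. Blinded adjudication in Section 7.2 covers index-infection readmissions and the scoring of medical errors. It does not cover SAE relatedness.

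**Step 5. Which events are graded.** Section 12.2.2 keeps readmissions out of SAE reporting unless the principal investigator decides otherwise, so most worsening never receives a grade. What remains includes deaths, life-threatening events and medical errors at harm levels F to I. Section 12.2.1 counts diagnostic mistakes and delayed care among such errors, which is where an absent visit could matter.

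**Step 6. What does not depend on the grade.** The outcome analyses in Section 9 do not use it. Readmissions and medical errors go to the DSMB as safety events (Section 12.2). The medical monitor assesses every SAE and the DSMB reviews SAEs at its scheduled meetings (Section 12.2.6).

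**The case against.** A reader might infer that the rule forces infection progression in the PRN arm to be classed as unrelated, so that the safety signal is lost. The documents do not support that. Not Related requires a clear relation to other factors. Possibly Related covers the same event whenever the investigator is less certain, and it is sufficient for an unanticipated problem. The medical monitor sees every SAE whatever the site's grade, and halting enrollment turns on the monitor's own belief. Late recognition is also captured as readmission, as blinded index-infection readmission, and as medical error. All of this stands, and it limits the point to case-level escalation.

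Nor does it follow that every SAE in both arms is Possibly Related. The class asks for compatible timing, and an event before discharge or within hours of it need not be compatible with the absence of a visit that would have fallen within 7 days.

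A further objection is that expectedness is the firmer block, because Section 12.2.3 makes any symptom of the index infection expected. That is a separate restriction and it is real; correcting relatedness alone would not open the routes for such symptoms. But the two conditions must hold together, so correcting expectedness alone would not be enough either. Section 12.2.3 also calls an SAE unexpected when its nature, severity or frequency departs from the described risks, and Section 11.5 describes only loss of confidentiality. On that sentence a severe progression could be unexpected, and relatedness would then decide.

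Finally, any replacement test still rests on an unblinded investigator's judgement. That is so, but it would at least ask the relevant question.

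**Conclusion.** The concern holds in limited form. The classes treat the child's clinical state as an alternative to the intervention, although the harm the protocol foresees acts through it. Progression of the index infection can be graded Not Related, can hardly ever be graded Probably Related, and may be graded differently by different investigators on the same facts.

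The reach is narrow: case-level escalation under Sections 12.2.5 and 12.2.6 of SAEs not handled as readmissions. These are likely to be few but are the most serious events in the trial. The protocol gives no expected number, so no numerical size can be put on it. The trial's conclusions on readmission and on the safety outcomes are unaffected.

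The verdict rests on two readings. First, late recognition as the mechanism is taken from Table 4 and Section 4.5; the non-inferiority hypothesis in Section 3.1 does not itself state a mechanism. Second, the medical monitor is assumed to work from the same criteria, since the protocol gives no others. The change is worth making, but the trial does not fail without it.

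**What to change.** Amend Section 12.2.3 in three respects:

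1. Define relatedness to the follow-up recommendation, in both arms. An SAE is related, to whatever degree, if attending or not attending a follow-up visit could plausibly have changed whether it occurred, when, or how severely. This includes harm from tests or treatment arising at a visit.
2. State that progression of the index infection is not by itself grounds for Not Related.
3. Make the three classes mutually exclusive, so that the same facts cannot satisfy two of them.

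The expectedness definition needs its own review and is not corrected by this change.

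The cost is protocol wording and a line in site training. Somewhat more SAEs will be graded possibly related and reviewed. No outcome, analysis or sample size changes.
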